### **13.5.2. Safety**

#### **13.5.2.1. Analysis Population**

The safety population will be defined as all subjects who received at least 1 dose of study treatment.

#### **13.5.2.2. Methods of Analysis**

All AEs, SAEs, laboratory abnormalities, physical examination results, and vital signs will be evaluated for safety.

#### **13.5.2.3. Adverse Events**

The incidence of treatment-emergent AEs will be summarized by severity and by relationship to study treatment. The summary tables will include AEs by system organ class as well as by preferred term within each system organ class. AEs will be coded using the Medical Dictionary for Regulatory Activities.

#### **13.5.2.4. Laboratory Data**

Laboratory data will be summarized using shift tables. Shifts from baseline to high/low status for hematology and blood chemistry parameters will be presented. In addition, the shift from baseline to the maximum post-baseline value and the shift from baseline to the minimum post-baseline status will be presented for each laboratory test by treatment group. Summary statistics for actual values and change from baseline will also be presented for quantitative laboratory data.

#### **13.5.2.5. Physical Examination Results**

A listing of subjects with normal status at baseline but abnormal status at any time after the date of the first dose will be presented.

#### **13.5.2.6. Vital Signs**

The analysis of vital signs will focus on the incidence of clinically relevant abnormalities. The number of subjects evaluated and the number and percentage of subjects with clinically relevant post-baseline abnormalities (Table 2: ) will be presented. Summary statistics for actual values and change from baseline will also be presented.

CONFIDENTIAL

The information contained herein may not be used, disclosed, or published without the written consent of  
Biogen MA Inc.

[REDACTED]

[REDACTED]

[REDACTED]

[REDACTED]

[REDACTED]

[REDACTED]

[REDACTED]

CONFIDENTIAL

The information contained herein may not be used, disclosed, or published without the written consent of Biogen MA Inc.

### **13.7. Interim Analysis**

There are no planned interim analyses for this study.

CONFIDENTIAL

The information contained herein may not be used, disclosed, or published without the written consent of  
Biogen MA Inc.

## **14. ETHICAL REQUIREMENTS**

Biogen, [REDACTED] and the Investigator must comply with all instructions, regulations, and agreements in this protocol and applicable International Conference on Harmonisation (ICH) guidelines and conduct the study according to local regulations. The subject's privacy; physical, mental, and social integrity; and the confidentiality of his or her personal information will be strictly respected in accordance with the World Medical Association Declaration of Helsinki.

### **14.1. Institutional Review Board/Ethics Committee**

The Investigator must obtain IRB/EC approval of the protocol, ICF, and other required study documents prior to starting the study.

If the Investigator makes any changes to the ICF, Biogen must approve the changes before the ICF is submitted to the IRB/EC. A copy of the approved ICF must be provided to Biogen. After approval, the ICF must not be altered without the agreement of the relevant IRB/EC and Biogen.

It is the responsibility of the Investigator(s) to ensure that all aspects of institutional review are conducted in accordance with current governmental regulations.

Biogen must receive a letter documenting IRB/EC approval, which specifically identifies the protocol, tracking number, and ICF version, prior to the initiation of the study. Protocol amendments will be subject to the same requirements as the original protocol.

A progress report must be submitted to the IRB/EC at required intervals and not less than annually. Documentation of the submission must be provided to Biogen.

At the completion or termination of the study, the investigational site must submit a close-out letter to the IRB/EC and Biogen.

### **14.2. Subject Information and Consent**

Prior to performing any study-related activities under this protocol, including screening tests and assessments, written informed consent with the approved ICF must be obtained from the subject or subject's legally authorized representative, as applicable, in accordance with local practice and regulations.

The background of the proposed study, the procedures, the benefits and risks of the study, and that study participation is voluntary for the subject must be explained to the subject (or the subject's legally authorized representative). The subject must be given sufficient time to consider whether to participate in the study.

A copy of the signed and dated ICF must be given to the subject or the subject's legally authorized representative. Confirmation of a subject's informed consent must also be documented in the subject's medical record prior to any testing under this protocol, including screening tests and assessments.

The signed ICF will be retained with the study records. Local regulations must be complied with in respect to the final disposition of the original (wet signature) and copies of the signed and dated ICFs.

CONFIDENTIAL

The information contained herein may not be used, disclosed, or published without the written consent of  
Biogen MA Inc.

### **14.3. Subject Data Protection**

Prior to any testing under this protocol, including screening tests and assessments, candidates must also provide all authorizations required by local law (e.g., PHI authorization in North America).

The subject will not be identified by name in the CRF or in any study reports, and these reports will be used for research purposes only. Biogen, its partner(s) and designee(s), ECs, and various government health agencies may inspect the records of this study. Every effort will be made to keep the subject's personal medical data confidential.

### **14.4. Compensation for Injury**

Biogen maintains appropriate insurance coverage for clinical trials and will follow applicable local compensation laws.

### **14.5. Conflict of Interest**

The Investigators should address any potential conflicts of interest (e.g., financial interest in the Sponsor) with the subject before the subject makes a decision to participate in the study.

### **14.6. Registration of Study and Disclosure of Study Results**

Biogen will register the study and post study results regardless of outcome on a publicly accessible website in accordance with the applicable laws and regulations.

CONFIDENTIAL

The information contained herein may not be used, disclosed, or published without the written consent of  
Biogen MA Inc.

## **15. ADMINISTRATIVE PROCEDURES**

### **15.1. Study Site Initiation**

The Investigator must not screen any subjects prior to completion of a study initiation visit, conducted by Biogen or designee. This initiation visit will include a detailed review of the protocol and study procedures.

### **15.2. Quality Assurance**

During and/or after completion of the study, quality assurance officers named by Biogen or the regulatory authorities may wish to perform on-site audits. The Investigator will be expected to cooperate with any audit and to provide assistance and documentation (including source data) as requested.

### **15.3. Monitoring of the Study**

Biogen or its designee representatives may conduct onsite visits at the study facilities for the purpose of monitoring various aspects of the study. The Investigator must agree to Biogen-authorized personnel having direct access to subject (or associated) files for the purpose of verifying entries made in the CRF, and assist with their activities, if requested. Adequate space and time for monitoring visits should be made available by the Investigator or study staff. The site must complete the CRFs in a timely manner and on an ongoing basis to allow regular review by the study team.

### **15.4. Study Funding**

Biogen is the Sponsor of the study and is funding the study. All financial details are provided in the separate contract(s) between the institution, Investigator, and Biogen.

### **15.5. Publications**

Details are included in the clinical trial agreement for this study.

CONFIDENTIAL

The information contained herein may not be used, disclosed, or published without the written consent of  
Biogen MA Inc.

## **16. FURTHER REQUIREMENTS AND GENERAL INFORMATION**

### **16.1. External Contract Organizations**

#### **16.1.1. Contract Research Organization**

██████████ will be responsible for administrative aspects of the study including, but not limited to, study initiation, monitoring, and management of SAE reports and data management. Before subjects are screened at each study site, the contract research organization (CRO) will review study responsibilities with the Investigators and other study site staff, as appropriate.

#### **16.1.2. Electronic Data Capture**

Subject information will be captured and managed by study sites on electronic CRFs by a web-based EDC tool developed and supported by EDC vendor and configured by Biogen.

#### **16.1.3. Central Laboratories for Laboratory Assessments**

A central laboratory has been selected by Biogen to analyze hematology, blood chemistry, immunology and urine samples collected for this study.

#### **16.1.4. Central Facility for MRI Assessments**

██████████ has been selected by Biogen to read and interpret all MRIs.

All of the MRI scans with and without Gd will be evaluated at a central MRI reading center, ██████████. All investigational sites will be required to send a test scan of a healthy volunteer subject to the MRI central reading center for evaluation in order to ensure that the site's scanning techniques are appropriate. This review will take place before the investigational site is permitted to enroll any subjects into the study.

MRI digital data should be sent over the internet, if possible. If not possible, MRI digital data can be sent on a compact disk.

Refer to the MRI Acquisition and Procedures Manual for more information and detailed instructions.

### **16.2. Advisory Committee**

An Advisory Committee will be formed to provide scientific and medical direction for the study and to oversee the administrative progress of the study. The Advisory Committee will meet at regular intervals to monitor subject accrual and to monitor compliance with the protocol at individual study sites. The Advisory Committee will determine whether the study should be stopped or amended.

Members of the Advisory Committee will include the Medical Director, Clinical Trial Manager, and Project Statistician from Biogen (and/or their designees), and participating Investigators. Biogen will designate one of the participating Investigators to be the Chairperson of the Advisory Committee.

CONFIDENTIAL

The information contained herein may not be used, disclosed, or published without the written consent of Biogen MA Inc.

### **16.3. Data Safety Monitoring Board**

An independent Data Safety Monitoring Board (DSMB) will be formed to monitor benefit/risk during the course of the trial. The DSMB will review all AEs, clinical observations, vital signs, and laboratory tests for all subjects. The DSMB may also request and review data and monitor efficacy endpoints. The DSMB will be comprised of members with appropriate expertise who are all independent of the Sponsor. Members will not be blinded to subject treatment assignment as this is an open-label trial. Investigational sites will be notified of any relevant safety findings that may jeopardize subject safety. The DSMB will meet routinely throughout the study duration. A charter will be established between Biogen and the DSMB to outline the DSMB's responsibilities and procedures.

### **16.4. Changes to Final Study Protocol**

All protocol amendments must be submitted to the EC and Regulatory Authorities if required by local law. Protocol modifications that affect subject safety, the scope of the investigation, or the scientific quality of the study must be approved by the EC before implementation of such modifications to the conduct of the study. If required by local law, such modifications must also be approved by the appropriate regulatory agency prior to implementation.

However, Biogen may, at any time, amend this protocol to eliminate an apparent immediate hazard to a subject. In this case, the appropriate regulatory authorities will be notified subsequent to the modification.

In the event of a protocol modification, the subject consent form may require similar modifications (see Sections 14.1 and 14.2).

### **16.5. Institutional Review Board/Ethics Committee Notification of Study Completion or Termination**

Where required, the Health Authorities and IRBs/ECs must be notified of completion or termination of this study, and sent a copy of the study synopsis in accordance with necessary timelines.

### **16.6. Retention of Study Data**

The minimum retention time for study records will meet the strictest standard applicable to that site, as dictated by any institutional requirements or local laws or regulations. Prior to proceeding with destruction of records, the Investigator must notify Biogen in writing and receive written authorization from Biogen to destroy study records. In addition, the Investigator must notify Biogen of any changes in the archival arrangements including, but not limited to, archival at an off-site facility or transfer of ownership if the Investigator leaves the site.

CONFIDENTIAL

The information contained herein may not be used, disclosed, or published without the written consent of  
Biogen MA Inc.

5.4.2 Clinical Laboratory Data11

5.4.3 Vital signs12

1 STUDY OBJECTIVES AND ENDPOINTS

1.1 Primary Objective and Endpoint

The primary study objective is to evaluate the effects of treatment with daclizumab beta on proportion of subjects relapse-free at Month 6, in RRMS subjects who switched from treatment with natalizumab to daclizumab beta due to safety concerns.

The primary endpoint in relation to this objective is the proportion of subjects relapse-free at Month 6, in RRMS subjects treated with daclizumab beta who switched from treatment with natalizumab.

1.2 Secondary Objectives and Endpoints

The secondary objectives are to evaluate the effects of daclizumab beta on the following:

- Multiple Sclerosis (MS) relapse activity including annualized relapse rate (ARR) and the proportion of subjects experiencing relapses requiring hospitalization and/or steroid treatment.
- MS-related outcomes measured using magnetic resonance imaging (MRI).
- Safety and tolerability in subjects previously treated with natalizumab.

The secondary endpoints are:

- The proportion of subjects relapse-free at Month 12.
- The proportion of subjects experiencing relapse requiring hospitalization and/or steroid treatment at Month 12.
- The ARR at Month 12.
- The number of new gadolinium enhanced (Gd+) and T1 hypointense lesions at Month 6 and Month 12 on MRI.
- The number of new or newly enlarged T2 hyperintense lesions at Month 6 and Month 12 on MRI.
- The permanent discontinuation rate of daclizumab beta at Month 12.
- The incidence of adverse events (AEs) and serious adverse events (SAEs) including clinically relevant.

1.3 Exploratory Objectives and Endpoints

The exploratory objectives of this study in this study population are to evaluate the effects of daclizumab beta on the following:

- 

[figure not shown]
- [REDACTED]
- [REDACTED]
- [REDACTED]

The exploratory endpoints of the study are:

- [REDACTED]
- [REDACTED]
- [REDACTED]
- [REDACTED]
- [REDACTED]
- [REDACTED]
- [REDACTED]
- [REDACTED]
- [REDACTED]

2 STUDY DESIGN AND SAMPLE SIZE

This is a multicenter, open-label study of daclizumab monotherapy in subjects with RRMS who were previously treated with natalizumab for at least 12 months. Subjects will be enrolled over an approximately 12-month period. Subjects discontinuing from natalizumab treatment due to safety concerns will commence treatment with daclizumab beta following consent and evaluation of eligibility. Subjects will initiate treatment with daclizumab beta at 28 (+3) days following the last infusion of natalizumab. Assessments will be completed at enrollment, baseline, Month 1, Month 3, Month 4, Month 6, Month 9 and Month 12.

The duration of subject participation will be up to 16 months, including a 28 (+3) day screening period, treatment with daclizumab beta for up to 12 months, and an additional safety follow-up visit performed remotely 4 months after last study treatment dose. Subjects having tentative disability progression near the end of the core study (e.g., Month 12) will attend additional follow-up visits 12 and 24 weeks later to confirm progression. This study will enroll approximately 100 subjects. The sample size is estimated based on the proportion of subjects who are relapse-free at Month 6.

On March 2, 2018, daclizumab beta has been voluntarily withdrawn from the global market and the drug supply to patients has been stopped. As a result SUSTAIN has been terminated. An abbreviated clinical study report will be developed based on the patient data available upon the withdrawal and from the safety follow-up.

3 ANALYSIS POPULATIONS

The full analysis set (FAS) will include all subjects who receive at least one dose of daclizumab. This dataset will be used for all analyses.

4 GENERAL CONSIDERATIONS

The SUSTAIN study was terminated early by sponsor upon the withdrawal of daclizumab from the global market after approximately 30 subjects were enrolled in study. Because the study was not fully enrolled and there was limited follow-up time, some endpoints will no longer be analyzed and some endpoints and outcomes will be summarized in listings rather than data tabulations. Missing data in this study will not be imputed.

4.1 Treatment Period Definitions

Based on the schedule of assessment, we have the following definitions:

- **the first dosing date** is the date when the subject is first dosed;
- **the last dosing date** is the date of the last date the subject is dosed;
- **The end of study date** is the last visit date;

- **Treatment period, or, time on (study) treatment**, is defined as the time between the first dosing date and the last dosing date; it is calculated as the last dosing date minus the first dosing date + 1; also known as the time exposed to study drug;
- **Time on study, or study period**, is defined as the time between the first dosing date and the end of study date, calculated as the last visit date – the first dosing date + 1.

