## Efficacy and Safety of Daclizumab in Subjects with RRMS Switching from Natalizumab

1. Written informed consent must be obtained prior to start of the study.
2. Screening MRI should occur no later than 7 days prior to the first dose of daclizumab. For subsequent visits, MRI scan can be performed up to 4 days prior to the visit. Ad-hoc MRIs may be conducted as needed, such as in the event of a relapse to rule out PML diagnosis.
3. This is required only for females of child-bearing potential. A urine pregnancy test will be performed monthly.
4. Liver function tests (LFTs) are required to be performed monthly (either on-site or via home visits at Month 7, 8, 10 and 11, if applicable), and samples will be analyzed centrally for the purposes of this study. Results from either local or central LFT tests can be used for medical management of the patient and to determine whether dosing should continue or be suspended at the monthly dosing timepoint. In cases where local LFTs were performed, samples must also be collected for central analysis.
5. Liver function tests (LFTs) during the safety follow-up will be performed only if the subject is continuing daclizumab or if the subject is within 4 months since study treatment discontinuation, and monitoring is deemed appropriate by the Investigator; Abnormal AST/ALT values as described in the product label will lead to treatment suspension or discontinuation.
6. [REDACTED]
7. Samples will be analyzed centrally.
8. Daclizumab dosing will start at baseline and occur monthly until Month 11. Doses at baseline and Months 1, 2, 3, 4, 5, 6 and 9 will be administered in the clinic, and doses at Months 7, 8, 10 and 11 can be administered at home or in the clinic. Daclizumab dosing will not begin until a minimum of 28 days have passed since last natalizumab dose. Before a monthly dose of daclizumab is given, LFT results from a prior test performed within the previous 28 (+3) days must be reviewed by the Study Neurologist or their backup.
9. Subjects will be provided a dosing diary at the Month 6 and Month 9 visits to record observations for home dosing only; home dosing is possible for Month 7, 8, 10, and 11. A window of  $\pm 4$  days applies to daclizumab dose even if it is done at home; subjects should be appropriately instructed on daclizumab self-administration using the autoinjector.

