## **10.5. Treatment Schedule Modification**

Subjects who experience a significant change in their medical status (e.g., neurological worsening/suspected MS relapse, possible injection-site reaction, infection, cutaneous event, fever, abdominal pain, persistent diarrhea, jaundice, nausea, vomiting, pruritus) must contact the Study Neurologist as soon as possible and no more than 48 hours after symptom onset. The subject should then be evaluated by the Study Neurologist within no more than 72 hours for physical and neurological assessments and further treatment recommendations if appropriate. These subjects should not administer additional daclizumab until they have been evaluated by the Study Neurologist or their backup

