5 STATISTICAL ANALYSES

5.1 Primary Analysis

Definition of relapses. Relapses are defined as new or recurrent neurological symptoms not associated with fever or infection, lasting at least 24 hours, and accompanied by new objective neurological findings upon examination by the Examining Neurologist. Protocol-defined relapses up to the end of treatment period visit will be included in the primary analyses. New or recurrent neurological symptoms that occurred less than 30 days following the onset of a protocol-defined relapse will be considered part of the same relapse (i.e., relapses with onset days ≤ 29 days of one another, will be counted as 1 relapse).

Censoring. If a subject prematurely discontinues the treatment and the subject does not experience a protocol-defined relapse prior to discontinuation, the subject will be censored on the last dosing date.

Analysis method. The number of relapses per subject will be summarized. The proportion of subjects who are relapse-free at 6 months will be estimated as 1 minus the cumulative

probability of relapses from the Kaplan-Meier product limit method. The time to relapse is the number of days from the first dosing date to the date of first relapse, or end of treatment period, whichever comes first. Time to first relapse will be summarized by 10th, 25th and 50th percentile.

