5.2.2 Analysis for Annualized Relapse Rate (ARR)

ARR will be analyzed for both treatment period and study period. Please see section 4.1 for their definitions.

The number of relapses observed during the treatment period (or during the study period) will be summarized as a categorical variable (number of relapse being 0, 1, 2, 3 and ≥ 4).

The unadjusted relapse rate will be calculated as the total number of relapses observed divided by the total number of days on treatment (or on study) multiplied by 365.25.

If there is sufficient data, the adjusted mean annualized relapse rate and its 95% confidence interval (CI) during the treatment period will be estimated by a negative binomial model; proper covariates are adjusted in the model. The logarithmic transformation of the number of days in the study will be included in the model as the “offset” parameter. If the data is under-dispersed or if the negative binomial regression model does not converge, a Poisson model will be used instead of the negative binomial regression model. Dispersion will be evaluated from the Pearson Chi-Square statistic. If the ratio of the Pearson Chi-Square statistic to the degrees of freedom is < 1 then a Poisson regression model will be used.

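### SAP 4.1 closes the treatment period on the day of the last monthly injection, so time on treatment is understated and a relapse that ends dosing can drop out of the on-treatment estimates

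*SAP*

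**What the plan says.** SAP 4.1 defines the treatment period by its end dates: "it is calculated as the last dosing date minus the first dosing date + 1; also known as the time exposed to study drug". It also defines a study period, which "is defined as the time between the first dosing date and the end of study date", the latter being the last visit. The footnotes to the protocol's schedule of assessments set the dosing pattern: "Daclizumab dosing will start at baseline and occur monthly until Month 11", which is 12 doses.

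Three SAP rules depend on these definitions.

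- **Primary analysis (5.1).** Time to relapse stops at the first relapse or the end of the treatment period, whichever is earlier. A subject who discontinues early without a prior relapse is handled thus: "the subject will be censored on the last dosing date". The same section says: "Protocol-defined relapses up to the end of treatment period visit will be included in the primary analyses". Section 4.1 defines no such visit.
- **ARR (5.2.2).** It is reported for both periods, as the "total number of relapses observed divided by the total number of days on treatment (or on study) multiplied by 365.25".
- **Adjusted ARR (5.2.2).** The treatment-period model, fitted only if data suffice, takes as its offset the log of days in the study.

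Protocol 13.4.1 instead ran the relapse clock to the end of study. Protocol 10.5 tells subjects with a suspected relapse to contact the Study Neurologist and adds: "These subjects should not administer additional daclizumab until they have been evaluated by the Study Neurologist or their backup".

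**The concern.** An injection given monthly does not stop acting on the day it is given, and the SAP accepts this elsewhere: 5.4.1 treats adverse events as treatment-emergent until 180 days after the last dose. Time after the last injection therefore counts as on drug for harm but not for relapse.

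The interval lost is also not a random piece of follow-up. If a subject relapses and receives no further dose, the relapse necessarily begins after the last dosing date. It then leaves the numerator of the treatment-period ARR. On the literal 5.1 clock the subject enters the Kaplan-Meier estimate as censored and relapse-free. Censoring caused by the event itself can only raise the relapse-free proportion. The SAP plans no second version of the primary estimate over the study period that would reveal the difference.

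**Working it through.** **The plan's own figure.** Protocol 13.1 gives 95% CI half-widths for n = 90. The formula 1.96 × √(p(1−p)/90) gives 8.26% at p = 0.80 and 6.71% at p = 0.88, matching the stated 8.3% and 6.7%. The concern does not rest on these figures, but they are a yardstick. At the midpoint p = 0.84 the half-width is 7.6 points.

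**Time on treatment.** One interval is 365.25/12 = 30.4 days. With k doses the SAP records (k−1) × 30.4 + 1 days; last dose plus one interval is k × 30.4 days (rounded below).

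| Doses | SAP days | Through last interval | Shortfall |
|---|---|---|---|
| 12 | 336 | 365 | 7.9% |
| 6 | 153 | 183 | 16.4% |
| 3 | 62 | 91 | 31.9% |
| 1 | 1 | 30 | 96.7% |

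**Treatment-period ARR.** Let q be the share of relapses after which no dose is given. The documents do not state q, so the full range 0 to 1 is used. Two illustrative rates are also assumptions: 0.22 per year (the daclizumab arm of the active-controlled trial in protocol 5.1.4) and 0.575 per year (25% relapsing in 6 months after a switch to fingolimod, protocol 5.2: −2 × ln 0.75). Each scenario simulates 400,000 subjects with monthly doses and a constant hazard. Relapses and days both stop at the last dose.

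| q | True 0.22 | True 0.575 |
|---|---|---|
| 0 | 0.220 | 0.572 |
| 0.25 | 0.167 | 0.435 |
| 0.5 | 0.111 | 0.292 |
| 1 | 0.000 | 0.000 |

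The fall is close to the fraction q. Stopping subjects at random after 1 to 12 doses, as a sponsor termination might, leaves the results essentially unchanged.

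**Primary estimate, strict reading.** Let π be the monthly relapse probability. Relapses that end dosing are censored at the preceding dose, so the monthly hazard that is seen is π(1−q)/(1−πq), and the Month 6 estimate is (1 − that)^6. For an assumed true 84%, π = 1 − 0.84^(1/6) = 0.0286.

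- q = 0: 0.840.
- q = 0.25: hazard 0.0216, estimate 0.877.
- q = 0.5: hazard 0.0145, estimate 0.916.

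The two rates above bracket this: 0.896 becomes 0.921 or 0.946, and 0.750 becomes 0.805 or 0.865.

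**Opposite direction.** Suppose relapses are counted to a visit one interval after the last dose while days still end at the last dose. The rate is then too high by 365/336 = 1.09 (12 doses), 183/153 = 1.20 (6 doses) or 91/62 = 1.47 (3 doses).

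**Offset.** For a 12-dose subject, relapses from the treatment period modelled over days in the study multiply the rate by 336/366 = 0.92 if the last visit is Month 12, or by 336/458 = 0.73 if it is four months after the last dose.

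**The case against.** A reader might infer that the on-treatment ARR is biased downward in any case. The documents do not support that. Closing the period at the last dose removes days as well as relapses, so with a constant hazard and stopping unrelated to relapse the rate is right, as the q = 0 rows show. SAP 2 and 4 give exactly such a cause of stopping: the sponsor withdrew the drug.

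Nor does protocol 10.5 show that relapses end treatment. It is a hold pending evaluation within 72 hours, and relapse is not among the permanent-discontinuation criteria listed in 10.5.1. Some relapsing subjects may still stop, but the documents give no fraction.

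For the primary analysis, the censoring sentence covers only subjects without a relapse before discontinuation. A relapse that prompted discontinuation came first, and could be read as counted. That reading, and the sentence counting relapses to a closing visit, both conflict with a clock that has already stopped at the last injection. The text is ambiguous, so the strict-reading figures are one possible outcome, not the certain one.

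The relapses also do not vanish from the report. The study-period ARR includes those up to the last visit, protocol 7.2 collects relapses for four months after stopping, and SAP 5.2.1 lists those needing hospitalization or steroids. This mitigation stands for the ARR. It does not reach the primary estimate, which has no study-period version.

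**Conclusion.** Time on treatment is understated by about one dosing interval per subject under any reading; this needs no assumption beyond monthly dosing. The relative loss grows as courses shorten, which matters in a study terminated early with about 30 subjects enrolled.

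The effect on efficacy is conditional. The treatment-period ARR and, on the literal clock, the primary estimate can be biased in the drug's favour to the extent that relapse leads to stopping: an ARR lower by roughly the fraction q, and an assumed 84% relapse-free reading about 88% or 92% at q = 0.25 or 0.5. The latter shift, 7.6 points, equals the planned half-width at 84%. With 30 subjects fully followed, only 30 × 0.16 = 4.8 would be expected to relapse by Month 6, so losing one or two is visible. At q = 0 with a constant hazard there is no bias, and counting relapses to the undefined visit over shortened days would bias the ARR upward. That the direction depends on an undefined term is itself a reason to act. Severity: should-fix. The values of q, the relapse rates and the constant hazard are assumptions.

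**What to change.** Define one analysis window in SAP 4.1: from the first dosing date to the earlier of the last dosing date plus one dosing interval and the end of study date. Then:

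- Use it for the relapse count, the person-days, time on treatment and the primary clock.
- In 5.1, replace censoring on the last dosing date with censoring at the end of this window, and replace the undefined visit with the same window.
- State that any relapse with onset inside the window counts, including one that led to stopping.
- In 5.2.2, use log days in the window as the offset of the treatment-period model.

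Changing 4.1 alone is not enough, because the censoring sentence and the offset would keep the mismatch. In the simulation, taking both relapses and days through the last interval recovers the assumed rate, to simulation error, for every q from 0 to 1. No new data are needed. The cost is several SAP sentences and derived dates, and possibly a slightly less favourable relapse-free proportion.
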